## Abstract

## BACKGROUND:

At Emergency Medical Dispatch (EMD) centers, Resource Constrained Situations (RCS) where there are more callers requiring an ambulance than there are available ambulances are common. At the EMD centers in Uppsala and Västmanland, patients experiencing these situations are typically assigned a low-priority response, are often elderly, and have non-specific symptoms. Machine learning techniques offer a promising but largely untested approach to assessing risks among these patients.

#### **OBJECTIVES:**

To establish whether the provision of machine learning-based risk scores improves the ability of dispatchers to identify patients at high risk for deterioration in RCS.

#### DESIGN:

Multi-centre, parallel-grouped, randomized, analyst-blinded trial.

#### POPULATION:

Adult patients contacting the national emergency line (112), assessed by a dispatch nurse in Uppsala or Västmanland as requiring a low-priority ambulance response, and experiencing an RCS.

#### OUTCOMES:

Primary:

1. Proportion of RCS where the first available ambulance was dispatched to the patient with the highest National Early Warning Score (NEWS) score

Secondary:

- Difference in composite risk score consisting of ambulance interventions, emergent transport, hospital admission, intensive care, and mortality between patients receiving immediate vs. delayed ambulance response during RCS.
- Difference in NEWS between patients receiving immediate vs. delayed ambulance response during RCS.

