#### Hypotheses

Primary:

 The intervention results in a greater proportion of immediate ambulance responses in RCS being directed to the patient in the most critical condition as operationalized by subsequent NEWS value.

Secondary:

- The intervention improves differentiation with regards to a composite risk score consisting of ambulance interventions, abnormal initial ambulance findings, emergent transport, hospital admission, and mortality between patients receiving immediate vs. delayed ambulance response during RCS.
- 2. The intervention improves differentiation regarding NEWS between patients receiving immediate vs. delayed ambulance response during RCS.

Other pre-specified analyses:

- 1. Evaluation of overall personnel compliance with risk assessment instrument in intervention arm.
- 2. Evaluation of compliance in intervention arm cases where the model had a high vs low level of confidence.
- 3. Evaluation of improved/degraded compliance with risk assessment instrument over time as manifested by a slope change in a time series analysis of intervention group
- 4. Evaluation of spillover effects as manifested by a significant positive slope in a time series analysis of control group outcomes
- 5. Evaluation of change in risk assessment tool predictive value over time (covariate drift)
- 6. Evaluation of model calibration with regards to age, gender, and complaint category

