#### Intervention

The intervention is based on a risk assessment instrument validated in a previous study. (1) Since the publication of the validation study, the risk assessment instrument been further developed to include free-text notes entered by dispatchers, which were found to improve the performance of the models. The full source code of the tool employed in the study is freely available for replication purposes: https://github.com/[name]/openTriage.

The framework estimates the likelihood that a patient will be assessed by ambulance crews to 1) have abnormal initial findings, 2) be transported to the hospital with lights and sirens, 3) receive a prehospital intervention, and 4) be admitted to the hospital, or die within 30 days. Hospital outcome measures are based on the first hospital visit within 72 hours to capture hospital visits of non-conveyed patients. The predicted likelihood for each of the outcomes is then combined into a composite risk score, with the above outcomes weighted 4:2:1:1. In each RCS included in the intervention arm, the patient with the highest composite risk score will be indicated in a user interface integrated in the Alitis dispatching system used in Uppsala and Västmanland. A graphical indicator of model confidence will be integrated in the user interface, notifying users as to whether the model has a high- or low level of confidence in the prediction, with a cutoff value calibrated to include ca. 50% of patients in each group.

Development of the modelling framework will be frozen upon initiation of the main study phase. New predictor and outcome data will however continue to be captured and used to update the models in a quarterly monitoring and model updating process to ensure patient safety.

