#### Outcomes

The primary outcome of the study is based on the National Early Warning Score (NEWS) of each included patient based on the first set of vital signs captured by the ambulance crew upon arrival to the patient. If Ambulance vitals signs are missing (e.g., if a patient opted to take an alternate mode of transport to the hospital), the first set of vital signs obtained at ED triage will be used. NEWS was selected as the primary outcome of the study for two reasons: Firstly, NEWS is widely used in acute care, and has been thoroughly validated as being predictive of outcomes in a variety of adult patient cohorts.(7–10) Secondly, NEWS is based on patient vital signs, and is thus conceptually distinct from-, and prior in terms of causality to the outcome measures we employ to train the predictive models.

The latter reason is a subtle but important conceptual point which addresses two issues: Firstly, by selecting an evaluation measure which is not causally dependent on (or indeed identical to) the outcomes used to train the models, we minimize the possibility that assignment to the intervention or control arm in and of itself affects the evaluation measure (e.g., if it were communicated to the ambulance crew that a patient had a high risk of transport to the hospital using lights and sirens, this could influence the decisions of the crew, perhaps making them more likely to do so). Secondly, it addresses issues relating to AI system alignment. As suggested by the orthogonality thesis, the predictive performance of an AI system is independent of the goals of the system as a whole. (11) Operationalizing the need for a rapid ambulance response in terms of measurable outcomes is difficult, and we cannot assume that we have done so perfectly. Thus, it is appropriate that both the model and human decisions are evaluated in terms of a measure which in causally independent of either. In this way, we avoid giving the ML framework an unfair advantage over human dispatchers who may have internalized a different definition of patent risk and ambulance care need.

The first secondary outcome in the study is based on a composite score consisting of each of the four outcomes included in the risk assessment instrument. The outcomes will be weighted in a manner identical to the prediction framework. While this measure of intervention effectiveness suffers from

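### Does the Abstract's different component list leave the first secondary composite outcome open to two definitions?

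*Combined protocol and SAP*

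**What the plan says.** Four current places in the combined protocol and SAP itemise or define the composite.

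- **Abstract, Outcomes:** a "composite risk score consisting of ambulance interventions, emergent transport, hospital admission, intensive care, and mortality".
- **Hypotheses, secondary 1:** a "composite risk score consisting of ambulance interventions, abnormal initial ambulance findings, emergent transport, hospital admission, and mortality".
- **Methods, Intervention:** the instrument predicts whether a patient will "have abnormal initial findings, 2) be transported to the hospital with lights and sirens, 3) receive a prehospital intervention, and 4) be admitted". In full, the fourth item is to "be admitted to the hospital, or die within 30 days". The predictions are combined "with the above outcomes weighted 4:2:1:1". On timing, "Hospital outcome measures are based on the first hospital visit within 72 hours".
- **Methods, Outcomes:** the first secondary outcome is a "composite score consisting of each of the four outcomes included in the risk assessment instrument", and "The outcomes will be weighted in a manner identical to the prediction framework".

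The Objectives section also describes the composite, but only in general terms (prehospital interventions and hospital outcomes). It is not a component list and does not mention intensive care.

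**The concern.** The Abstract does more than shorten the list. It adds a component, intensive care, that the definition does not contain, and it drops the one with the largest weight. Three of its five terms (admission, intensive care, mortality) are hospital or survival events, so someone who read only the Abstract would expect a score made up mainly of hospital outcomes. Under the Methods definition, half of the weight rests on what ambulance crews find on arrival.

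Two things would be at stake. If both lists were workable definitions, the composite could be chosen after the data were seen. And a report that follows the Methods could look, against the Abstract, as if one component had been swapped for another.

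**Working it through.** **Inputs.** The component lists come from the Abstract, Hypotheses, Intervention and Outcomes sections. The weights 4:2:1:1 come from Intervention and are taken in the order in which the outcomes are numbered there.

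**Step 1: the plan's own weights.** 4 + 2 + 1 + 1 = 8. The shares are:

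- abnormal initial findings: 4/8 = 50%
- lights-and-sirens transport: 2/8 = 25%
- prehospital intervention: 1/8 = 12.5%
- admission or 30-day death: 1/8 = 12.5%

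**Step 2: the lists side by side.**

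| Component | Abstract | Hypotheses | Intervention and Outcomes | Weight |
|---|---|---|---|---|
| Abnormal initial findings | absent | present | present | 4 |
| Emergent (lights-and-sirens) transport | present | present | present | 2 |
| Ambulance intervention | present | present | present | 1 |
| Admission or death | present, as two terms | present, as two terms | present, as one item with a 30-day horizon for death | 1 |
| Intensive care | present | absent | absent | none |

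The Abstract's terms cover (2 + 1 + 1)/8 = 4/8 = 50% of the weight. The other 4/8 = 50% has no term there, and one Abstract term has no weight. The Hypotheses list matches the Methods once admission and death are read as one item. The discrepancy is real and has been counted correctly.

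**Step 3: can the Abstract's version be computed?** A weighted composite needs components, weights, a horizon for death and a rule for which hospital visit counts. The Abstract gives only the components. Borrowing the Methods weights for the terms that match leaves 2:1:1, which sums to 4 (50%, 25%, 25%), and intensive care still has no weight. An analyst would have to invent one. Doing so would also break the rule in the Outcomes section that the score use the instrument's four outcomes and weighting. The Methods version needs nothing invented.

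**Step 4: what depends on the composite?** The primary outcome and the other secondary outcome use NEWS. The stated power of 0.8 at n = 1500 is for the proportion of situations in which the ambulance goes to the patient with the highest NEWS. With 750 per arm, 63.5% against 70.3%, and two-sided alpha 0.05 (stated for the Wilcoxon calculation and assumed to carry over), power is 0.7997, which reproduces the plan's figure. The composite does not enter that calculation.

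**The case for a change.** The strongest case for a change is that all four places are current text and no clause says the Methods override the Abstract. Naming a component that the definition lacks is not abbreviation. The Blinding section promises that analysis code will be written before final data extraction only as far as possible, so the code alone may not fix the definition. The Outcomes section also concedes that this composite has the weaknesses that led to NEWS being preferred as the primary measure, which is a reason to state its make-up consistently. The correction would cost almost nothing.

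The inconsistency itself stands, and so does the remark that a reader who stops at the Abstract will form the wrong picture. The consequences do not follow. The Abstract is not the only itemised description: the Hypotheses section lists the components and Intervention numbers them. The choice between composites is not real either, because only one is fully specified. The Blinding section also has the analyst work with coded treatment groups and the code published, which leaves little room to pick a definition by its result. The 50% figure is a share of nominal weight points. It is not a share of the score's variance or of any treatment contrast, and without component frequencies the documents support no statement about an effect on the result.

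The Version History notes that version 1.1 added ambulance staff's initial assessment to the model outcomes, so the Abstract bullet may simply not have been refreshed. That is an inference, and it would not explain the intensive care term. Intensive care might be redundant wording within hospital admission, but the documents do not say so.

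**Conclusion.** This is a clerical slip in one summary bullet: one term too many and one too few, the missing one carrying 4 of 8 weight points. The Methods settle the definition, the Hypotheses agree with it, and the composite computed by following them is the same with or without a corrected Abstract. No analysis, result or conclusion changes, and the NEWS primary outcome, the NEWS secondary outcome, the sample size and the power are untouched. Anyone revising the document for another reason could align the bullet, but the statistical plan does not need it.

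This rests on two assumptions: that the weights follow the numbered order in Intervention, which is the plain reading, and that analysts work from the Methods definition rather than from the Abstract, which is ordinary practice and the only way to compute the score without inventing a weight.

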#### INTERVENTION:

A machine learning model will estimate the risk associated with each patient involved in the RCS, and propose a patient to receive the available ambulance. In the intervention arm only, the assessment will be displayed in a user interface integrated into the dispatching system.

#### TRIAL SIZE:

1500 RCS each consisting of multiple patients randomized 1:1 to control and intervention arms

## Version History:

1.0 - Initial version (2020-09-14)

1.1 - Post pilot study (2021-01-25)

- Updated outcomes used in risk assessment models to include ambulance staff initial assessment results
- Simplified primary hypothesis to improve interpretability and take advantage of additional statistical power granted by improved prediction models. (proportion test vs. rank sum test)

#### 1.2 - Post PRS review (2021-02-09)

• Add cover page

## Introduction

## Background

In many prehospital care systems, ambulance availability places constraints on the ability of Emergency Medical Dispatch Centers (EMDCs) to immediately provide an ambulance response for all patients determined to require one. The stochastic nature of ambulance demand via the emergency hotline (In Sweden, 112) entails that any cost-effective ambulance system will from time to time experience Resource Constrained Situations (RCS) in which the number of patients requiring an ambulance response exceeds the number of available ambulances.

In this study, we define an RCS as a situation in which EMDC staff must select one of multiple patients awaiting an ambulance to receive an ambulance response – i.e., the RCS is a discrete event occurring at the point in time at which a dispatch decision must be made. An RCS can arise either due to an absolute lack of available ambulances, or due to the need to maintain readiness to respond to high-priority patients. In some RCS, non-clinical factors such as relative geographical distances between patients and ambulances, or the amount of time patients have been waiting may determine the appropriate patient to dispatch an ambulance to. In many situations however, prioritization decisions are made by weighing the clinical condition of patients against each other. Given the heterogeneous nature of the patient population served by prehospital care providers, this can often be a difficult and complex decision.

In previous research, a machine learning-based risk assessment instrument was developed and validated retrospectively in a cohort of patients receiving prehospital care. (1) These instruments predict the likelihood of a patient experiencing a given set of clinical outcomes, such as hospital admission or mortality, and combining these likelihoods into an overall risk score. In this study, these tools will be applied to stratify patient risks, and serve as a decision support tool with the aim of ensuring that the patient with the most acute medical condition receives an immediate ambulance response in each RCS.

While a number of machine learning based risk assessment tools have been proposed for use in healthcare and validated retrospectively (2–4), there are few prospective trials, and none regarding models for risk stratification in broad patient cohorts in emergency care. There is thus a great need to identify suitable use cases for these tools, and to demonstrate their effectiveness in achieving clinically important objectives. The need for this evidence must however be balanced with the need to maintain a high degree of patient safety.

## Objectives

This study aims to investigate whether the application of a machine learning-based risk assessment instrument improves the ability of dispatchers to identify and dispatch an ambulance to the most critically ill patient in an RCS. The criticality of the patient's condition will be operationalized primarily as the National Early Warning Score (NEWS) based on the first set of vital signs obtained by the ambulance, and secondarily based on a composite risk score consisting of prehospital interventions and hospital outcomes.

#### Hypotheses

Primary:

 The intervention results in a greater proportion of immediate ambulance responses in RCS being directed to the patient in the most critical condition as operationalized by subsequent NEWS value.

Secondary:

- The intervention improves differentiation with regards to a composite risk score consisting of ambulance interventions, abnormal initial ambulance findings, emergent transport, hospital admission, and mortality between patients receiving immediate vs. delayed ambulance response during RCS.
- 2. The intervention improves differentiation regarding NEWS between patients receiving immediate vs. delayed ambulance response during RCS.

Other pre-specified analyses:

- 1. Evaluation of overall personnel compliance with risk assessment instrument in intervention arm.
- 2. Evaluation of compliance in intervention arm cases where the model had a high vs low level of confidence.
- 3. Evaluation of improved/degraded compliance with risk assessment instrument over time as manifested by a slope change in a time series analysis of intervention group
- 4. Evaluation of spillover effects as manifested by a significant positive slope in a time series analysis of control group outcomes
- 5. Evaluation of change in risk assessment tool predictive value over time (covariate drift)
- 6. Evaluation of model calibration with regards to age, gender, and complaint category

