#### Flow

Prior to initiation of the study, the risk assessment tool will be integrated into the dispatching interface used by all study centers. Ambulance directors will have overall responsibility for executing the study protocol, and be tasked with identifying RCS suitable for inclusion in the study.

Patients are included in the study upon the identification of an RCS involving eligible patients by the ambulance director at the point in time when an ambulance is available for immediate dispatch to one of the patients. Directors are instructed to carefully consider any non-clinical factors relevant to prioritizing the patients prior to randomization, and exclude any RCS where these factors would override a clinical determination per the above exclusion criteria. Upon selecting the relevant patients and pressing a button in the interface to compare the selected patients, the RCS will be randomly assigned to a study arm. In the control arm, the risk scores for each patient will be calculated and stored, but not displayed to the user. In the intervention arm, a mark will be displayed in the interface indicating which of the included patients has the highest risk score, along with a color-coded indicator of model confidence.

In both study arms, the ambulance director will confer with the nurses involved in triaging the patients to confirm which patient should receive the available ambulance. In the intervention arm, the ambulance director will note which patient was proposed by the machine learning framework in conference with the nurses. The director will then dispatch the available ambulance to the patient determined through this process to have the greatest need. This process will be repeated each time an ambulance becomes available.

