## Statistical analysis

To generate risk predictions, gradient boosting models are applied to patient demographics, structured CDSS data, and free-text noted embedded using the bag-of-words method. The methods are implemented in the openTriage platform as the 'uppsala\_alitis' framework (13) and have been validated in previous research.

The primary hypotheses will be evaluated using a standard two-sided test of proportions between the intervention and control groups. Investigating the secondary hypotheses will involve comparing outcomes for the patient receiving an ambulance immediately with patients for whom dispatch is delayed. Patients who do not receive an ambulance immediately may also potentially be included in later trials. This induces a potential that information from intervention arm comparisons could be used by dispatchers in control arm comparisons, thus biasing the results in the direction of a smaller intervention effect. Steps were taken in the development of the user interface to limit these "spillover" effects.

Figure 1 – Analysis flow

Additional pre-specified analyses 1-2 will be investigated by assessing the compliance of dispatchers with the risk assessment tool of risk scores in the high and low confidence groups of the intervention arm (calibrated based on pilot study data to consist of ca. 50% of assessments each), as well as dispatcher compliance, with the hypothesis that compliance will be higher in the high-confidence group.

Pre-specified analyses 3-5 will be examined using time-series analysis within a regression framework employing a variable representing the study month as the independent variable of interest. Analysis 6 will be conducted by constructing calibration curves for the risk model based on the patient groups of interest.

Missing vital sign data will be imputed using Multivariate imputation by chained equations. (14) As we found previously that between-imputation variance after calculating NEWS scores was minimal, the median of 5 imputed NEWS values will be used to assess the primary hypothesis. An analysis of loss to follow-up (i.e., patients requesting to withdraw from the study) will be performed.

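### The only spillover test in the readable text, a rising month slope in control outcomes, cannot detect stable carry-over through re-entering patients; a re-entry count would be a cheap, minor improvement

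*Combined protocol and SAP*

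**What the plan says.** Under Hypotheses, item 4 of the other pre-specified analyses is "Evaluation of spillover effects as manifested by a significant positive slope in a time series analysis of control group outcomes". Under Statistical analysis, items 3 to 5 are to be examined by regression "employing a variable representing the study month as the independent variable of interest".

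Statistical analysis also describes how spillover would arise: "Patients who do not receive an ambulance immediately may also potentially be included in later trials", so that "information from intervention arm comparisons could be used by dispatchers in control arm comparisons". It gives the direction, "biasing the results in the direction of a smaller intervention effect", and a mitigation: "Steps were taken in the development of the user interface to limit these" effects. Flow explains why re-entry can happen at any time: "This process will be repeated each time an ambulance becomes available". What an intervention-arm comparison reveals is limited: "a mark will be displayed in the interface indicating which of the included patients has the highest risk score", with a colour indicating model confidence.

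The readable text plans no count of RCS containing previously compared patients, no analysis by that history, and no statement of how a null slope will be read. Figure 1 is not available, so this describes the readable text only.

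**The concern.** The plan names one mechanism and tests for another. A slope over study months responds to something that builds up, such as dispatchers gradually learning from the tool. Re-entry of a waiting patient needs no build-up: it can occur on the first day and continue at much the same rate throughout. It then shifts the control proportion by a constant, which a slope does not register.

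What is at stake is how a small or null result is read. Readers would ask whether carry-over diluted the difference, and a null slope could be offered as reassurance that it cannot give.

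**Working it through.** **Inputs.** From Sample Size: 63.5% (control, pilot data), 70.3% (model, simulation), n = 1500, two-sided test of proportions, at most 2 years of data collection. Allocation is 1:1, so 750 RCS per arm. Alpha of 0.05 is stated there for the Wilcoxon calculation and is assumed to carry over. The documents give no re-entry share or strength of carry-over; both are assumed below.

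**1. The plan's own figure.** A two-sided test of 63.5% against 70.3% with 750 per arm has power 0.7997, which reproduces the stated 0.8. The planned difference is 70.3 − 63.5 = 6.8 points.

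**2. Why the slope misses stable carry-over.** The fitted slope is b = Σ(tᵢ − t̄)yᵢ / Σ(tᵢ − t̄)². Let a share f of control RCS be exposed, each gaining a fraction c of the effect, with f and c constant over time. Every expected yᵢ rises by f × c × 0.068. The contribution to b is that constant times Σ(tᵢ − t̄), which is zero. The expected slope is unchanged for any f and c, so a two-sided 5% test is significantly positive in about 2.5% of trials. This needs no assumed re-entry share.

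**3. Check by simulation.** 750 control RCS over 24 months, binary primary outcome, linear regression on month, 40,000 trials per scenario, RCS treated as independent:

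| Spillover in control arm | Significant positive slope |
|---|---|
| none | about 2.5% |
| stable, 10% of the effect | 2.7% |
| stable, all 6.8 points erased | 2.6% |
| growing from 0 to 50% of the effect | about 9% |
| growing from 0 to 100% of the effect | about 22% |

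The first three rows agree within simulation error. Even for gradual spillover, which the test is suited to, detection is low.

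**4. Maximum dilution.** If a remembered mark helps no more than a displayed one (c at most 1), dilution by this route is at most f × effect, where the effect is the undiluted one. For 6.8 points:
- f = 2%: 0.02 × 6.8 = 0.14 points
- f = 20%: 0.20 × 6.8 = 1.36 points

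**5. Illustrative power.** With c = 30% (assumed), f = 2% gives a difference of 6.8 × (1 − 0.006) = 6.76 points and power 0.795. With f = 20% it is 6.8 × (1 − 0.06) = 6.39 points and power 0.75.

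**6. What a restricted analysis can show.** Drop, in both arms, RCS with a patient previously compared in an intervention-arm RCS. Randomisation makes the expected share dropped equal in the two arms. The CI half-width is 1.96 × √[(0.635×0.365 + 0.703×0.297)/n] = 1.96 × √(0.4406/n). For the full-minus-restricted difference it is 1.96 × √[0.4406 × (1/n − 1/750)].

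| Share dropped | n per arm | Half-width (points) | Power for 6.8 points | Half-width, full minus restricted | Maximum dilution |
|---|---|---|---|---|---|
| 0% | 750 | 4.75 | 0.80 | – | – |
| 2% | 735 | 4.80 | 0.79 | 0.68 | 0.14 |
| 20% | 600 | 5.31 | 0.71 | 2.38 | 1.36 |

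The restricted estimate costs little precision at low shares, but at either end it is too imprecise to reveal the dilution by comparison with the full estimate. The count and the bound are therefore the more informative items.

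**The case against.** The plan recognises the problem: it names re-entry, gives the direction of the bias, reports interface measures and adds a check over time. Randomisation and the primary test remain valid. All of that stands, and it makes this a gap in measurement rather than in recognition. But interface measures do not show how much carry-over remained, and the check over time cannot show it either.

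The effect may also be negligible. Setting gives a median of 18 minutes from call to dispatch for low-priority responses, and Sample Size expects 2 eligible RCS per day. If RCS arrived independently, another would follow within 18 minutes with probability 1 − exp(−2 × 18/1440) = 2.5%, so at 1:1 about 1.2% of control RCS would be exposed. This is only indicative, because RCS may cluster in busy periods and RCS patients may wait longer than the median. Carry-over should also be weak: a marked patient who is sent does not re-enter, and a marked patient left waiting is one whose mark staff have already overridden. If pilot RCS had carry-over, part of it is already in the 63.5%. These points stand, and they argue for counting.

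The data are stored in any case, so a count could be made at reporting. True, but stating it beforehand settles how a null slope will be read.

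A reader might infer that the trial is materially underpowered through spillover. The documents do not support this: they give neither the re-entry share nor the strength of carry-over. A reader might also infer that the later start in Västmanland will distort the slope. Its size would rest on invented site differences, and the planned regression does not rule out a site covariate. Nor can it be said that the sponsor has no plan for repeat patients, since Figure 1 is not shown.

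**Conclusion.** The point holds as a minor improvement. In the readable text, the one spillover test has no power, beyond its false-positive rate of about 2.5%, against the stable form of the mechanism the plan itself describes. That follows from the algebra of the slope and does not depend on the assumed shares.

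The consequence is limited. The bias is towards the null, so a positive result is not undermined. For a small or null result, a null slope does not exclude carry-over. The dilution is unknown: 0.14 to 1.36 points at most if 2% to 20% of control RCS are exposed. That range is assumed, and the bound requires that a remembered mark help no more than a displayed one.

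**What to change.** 1. From the stored data, report the number and share of control RCS containing a patient earlier compared in an intervention-arm RCS, and how many of those patients had been marked highest-risk but not sent. Report exposed share times effect as the maximum dilution by this route, with its assumption. Because the effect in that product is the undiluted one, show it at least for the planned 6.8 points; a near-zero observed estimate would make the bound look trivially small.
2. Keep the month slope as a check for gradual learning only, and state that a null slope does not exclude stable carry-over.
3. As a supportive analysis, give the primary estimate with a 95% CI restricted, in both arms, to RCS with no patient previously compared in an intervention-arm RCS. That status is fixed before the current RCS is randomised, so the arms stay comparable. RCS whose patients have only control-arm history are kept, because no score was displayed for them. Note that the estimate is less precise and that a difference from the full estimate does not prove spillover, since the retained RCS may differ from the rest.

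The cost is a few sentences in the analysis section and some additional code. Data management / Collection already provides for storing dispatcher decisions, model predictions and allocation. Trial conduct, sample size and the primary test do not change.
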